8.5 Halting Rules

If a dose of study vaccine is considered significantly reactogenic (see below and Section 8.6.2), dose escalation and/or additional vaccinations will be suspended until reviewed by the SMC, Independent Medical Monitor, and IND sponsor (SVI). Any recommendation of the Independent Safety Monitor and/or SMC to resume or suspend further injections (either for an individual subject, an entire Group, or the full study) will be communicated in writing to the sponsor and Principal Investigator. All communications from the SMC will subsequently be forwarded by the investigators to the IRB.

The following criteria will be used to define significant reactogenicity:

- One or more participants experience a protocol defined SAE that is determined to be possibly, probably, or definitely related to a study vaccine, **OR**,
- One or more participants experience a protocol defined AESI that is determined to be possibly, probably, or definitely related to a study vaccine, **OR**,
- One or more participants experience a protocol defined Grade 3 hypersensitivity reaction that is possibly, probably or definitely related to a study vaccine, **OR**,
- Two or more participants experience a protocol defined Grade 2 hypersensitivity reaction that is probably or definitely related to a study vaccine, **OR**,
- Three or more participants in a single Group (i.e., Group 1, Group 2, etc.) experience the same objective physical finding or laboratory abnormality of Grade 3 or higher (with the exception of isolated Grade 3 erythema or swelling), that is determined to be probably or definitely related to a study vaccine, **OR**,
- Three or more participants in a single Group experience the same Grade 2 or higher safety laboratory abnormality or Grade 3 clinical AE that is possibly, probably or definitely related to a study vaccine.

The study will be double-blinded until all study subjects have completed their Day 208 visit, the safety and secondary immunogenicity outcomes (i.e., anti-Na-GST-1 and anti-Na-APR-1 (M74) IgG antibody results by ELISA) have been monitored and entered into the database, and the database has been “soft-locked” for interim analysis. After this milestone, the Sponsor and investigators will be unblinded. During the double-blinded part of the study, a study subject’s randomization code may be unblinded only for safety purposes. This is unlikely to occur, since once a vaccine is administered, knowing which vaccine was given is unlikely to influence the medical management of an AE. This procedure is therefore exceptional and any decision to unblind will be discussed with the sponsor, the Principal Investigator, the Independent Medical Monitor, and the SMC. If deemed necessary for urgent safety reasons, the Independent Medical Monitor, in consultation with the SMC (if possible in a timely manner), may unblind a specific subject without revealing the study blind to the investigators or the Sponsor. Any unblinding will be thoroughly documented. It is to be emphasized that the Independent Medical Monitor may put the study on hold at any time and discuss with the SMC. In the event that the investigators come to know the study code prior to final unblinding, the Principal Investigator must notify the Sponsor immediately. The reasons will be documented by the Principal Investigator and added to the study file.

The decision to completely unblind the study prior to Day 208 or permanently stop the study prior to the final study visit of all participating children will take the form of a formal recommendation by the SMC to the study Sponsor. The Principal Investigator must then notify the IRB of this decision.

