In order to review safety data at each dose of *Na-APR-1* (M74)/Alhydrogel[®] prior to testing it in combination with the point-of injection addition of GLA-AF, and to review safety data at each dose of *Na-APR-1* (M74)/Alhydrogel[®] prior to dose escalation, Groups will be enrolled and vaccinated in a staggered fashion. Conference calls between the investigators and the Safety Monitoring Committee (SMC) will be scheduled within the week prior to beginning vaccinations in Groups 2 and 3. A cumulative safety report will be submitted to the SMC before beginning vaccinations in these Groups that will include safety data from at least the first 14 days after vaccination of all subjects in the preceding Group. Written approval (via fax or email) to proceed to vaccinations of Groups 2 and 3 must be obtained from the SMC.

The SMC and Independent Medical Monitor will have access to the randomization code for the study, as they may wish to review the data in an unblinded fashion should significant safety questions arise prior to the final unblinding. The trial will not proceed to the next dose Group if any of the stopping criteria listed in **Section 8.5** are met or, in the clinical judgment of the SMC or the Independent Medical Monitor the next higher dose would pose an unacceptable safety risk to the subjects.

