8 ASSESSMENT OF SAFETY

8.1 Specification of Safety Parameters

Safety will be assessed by the frequency and severity of:

1. Study vaccine-related serious adverse events occurring from the time of the first study vaccination through approximately 9 months after the last study vaccination.
2. Solicited Adverse Events – reactogenicity events occurring on the day of each study vaccination through 14 days after each study vaccination:
 - a) Injection site reactions including erythema (redness), induration (hardness)/swelling, pain, and tenderness.
 - b) Systemic reactions including fever, myalgia (body aches/muscular pain exclusive of the injection site), arthralgia (joint pain exclusive of the injection site), headache, urticaria, vomiting, and nausea.
3. Clinical safety laboratory adverse events occurring from the time of each study vaccination through approximately 14 days after each set of vaccinations. Parameters to be evaluated include WBC, ANC, hemoglobin concentration, and platelet count; ALT; and, creatinine.
4. Unsolicited Adverse Events – non-serious adverse events occurring from the time of each study vaccination through approximately 28 days after each vaccination.
5. New-onset chronic medical conditions occurring from the time of the first study vaccination through approximately 9 months after the last study vaccination.
6. Adverse Events of Special Interest occurring from the time of the first study vaccination through approximately 9 months after the last study vaccination.

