Arthritis	Mild pain with inflammation, erythema or joint swelling – but not interfering with function	Moderate pain with inflammation, erythema or joint swelling – interfering with function, but not with activities of daily living	Severe pain with inflammation, erythema or joint swelling – and interfering with activities of daily living
Vasovagal episode (associated with a procedure of any kind)	Present without loss of consciousness	Present with transient loss of consciousness	Not Applicable
Cough	Transient-treatment no	Persistent cough; treatment responsive	Paroxysmal cough; uncontrolled with treatment
Bronchospasm, Acute	Transient; treatment; 70% - 80% FEV ₁ of peak flow	Requires treatment; normalizes with bronchodilator; FEV ₁ 50% - 70% (of peak flow)	No normalization with bronchodilator; FEV ₁ 25% - 50% of peak flow; or retractions present
Dyspnea	Dyspnea on exertion	Dyspnea with normal activity	Dyspnea at rest
Hypersensitivity	Transient flushing or pruritus without rash	Pruritic rash or mild urticaria	Symptomatic bronchospasm, with or without urticarial

Table 4: Assessment of Basic Body Function Adverse Event Severity

Vital Signs*	Mild (Grade 1)	Moderate (Grade 2)	Severe (Grade 3)
Tachycardia – beats per minute	115-130	131-150	>150
Bradycardia – beats per minute	55-59	50-54	<50
Hypertension** (systolic, mm Hg)	126-135	136-145	>145
Hypertension** (diastolic, mm Hg)	86-90	91-96	>96
Hypotension	Symptomatic, oral fluids not required	Symptomatic, corrected with oral fluid replacement	Symptomatic, IV fluids indicated

*Subject should be at rest for measurement of vital signs

**With repeat testing at same visit

Table 5: Assessment of Laboratory Adverse Event Severity

HEMATOLOGY	Grade 1 (Mild)	Grade 2 (Moderate)	Grade 3 (Severe)
Hemoglobin	8.2 – 9.2 g/dL	7.1 – 8.1 g/dL	<7.0 g/dL
Platelets	110,000 130,000/mm ³	– 90,000 109,999/mm ³	– <90,000/mm ³
WBCs (increase)	13,800 17,000/mm ³	– 17,001 20,000/mm ³	– <20,000/mm ³
WBCs (decrease)	2500 – 4200/mm ³	1500 – 2499/mm ³	<1500/mm ³
ANC (decrease)	750 – 1000/mm ³	500 – 749/mm ³	<500/mm ³
CLINICAL CHEMISTRIES	Grade 1	Grade 2	Grade 3
Serum creatinine	1.2 – 1.4 mg/dL	1.5 – 1.7 mg/dL	>1.8 mg/dL or requires dialysis
ALT	48 – 105 U/L	106 – 220 U/L	>220 U/L

All local (injection-site) reactions occurring within the first 14 days after vaccination will be considered definitely related to vaccination.

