8.6.2 Safety Monitoring Committee (SMC)

At least three individuals will be selected to serve as the study Safety Monitoring Committee (SMC) to advise the Sponsor and the study investigators on the trial. All SMC members will be independent from the Sponsor and study site. The SMC's primary responsibility will be to monitor subject safety. The Principal Investigator is responsible for ensuring that the SMC is aware of all new safety information. The SMC will periodically review data on safety and enrollment, and will review cumulative safety data for evidence of study related AEs, adherence to the protocol, and factors that may affect outcome or study data such as protocol violations and losses to follow up.

Cumulative safety data reports from the trial will be submitted to the SMC before beginning vaccinations in Group 2 and Group 3 of the study. These safety data reports will include data from at least the first 14 days after first vaccination of all subjects in the prior Group. After the third and final vaccination has been administered to all cohorts, additional safety and immunology results and reports will be submitted to the SMC as they become available.

Conference calls between the investigators and the SMC will be scheduled at least one week prior to beginning vaccinations in Group 2 and Group 3 of the study. If no criteria for halting the study are met (see Section 8.5 above) vaccinations will proceed with approval from the SMC.

Written approval (via fax or email) to proceed to vaccinating Group 2 and Group 3 must be obtained from the SMC prior to vaccine administration. Both the SMC and IMM will have access to the randomization code, as they may wish to review the data in an unblinded fashion should significant safety questions arise prior to the final unblinding of the study.

It is the Principal Investigator's (or designated agent) responsibility to ensure that the SMC reviews the current safety data (grouped by dose cohort), study protocol, and any other requested documents at its meetings. Occurrence of an SAE will be reported to the SMC at the same time

that it is reported to the IRB. Additionally, any new information that may adversely affect the safety of the subjects or the conduct of the study will be submitted to the SMC as it becomes available.

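### Section 8.5: the erythema/swelling exemption in the fifth halting criterion is cancelled by the sixth, and the criteria on hypersensitivity do not say which table grades urticaria

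*Combined protocol and SAP*

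**What the plan says.** **Halting criteria (Section 8.5).** Meeting any one of six criteria defines significant reactogenicity.

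- The third is met by one child with a "protocol defined Grade 3 hypersensitivity reaction that is possibly, probably or definitely related to a study vaccine".
- The fourth is met by two children with a "protocol defined Grade 2 hypersensitivity reaction that is probably or definitely related to a study vaccine".
- The fifth needs three children of one Group with the same objective finding or laboratory abnormality of at least Grade 3, rated probably or definitely related, "with the exception of isolated Grade 3 erythema or swelling".
- The sixth needs three children of one Group with "the same Grade 2 or higher safety laboratory abnormality or Grade 3 clinical AE", rated possibly related or higher. It has no exemption.

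**Relatedness and grading (Sections 8.1 and 8.2.2).** The rule for local events is: "All local (injection-site) reactions occurring within the first 14 days after vaccination will be considered definitely related to vaccination". Solicited systemic events include "arthralgia (joint pain exclusive of the injection site), headache, urticaria, vomiting, and nausea". Table 2, for solicited events, grades urticaria by the treatment needed. Table 3, headed as covering unsolicited events, has the only row named hypersensitivity and grades it by clinical sign.

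**Consequence.** Sections 4.3.6 and 8.5 describe suspension until review, after which vaccination may be recommended to resume. Section 3 says "The trial will not proceed to the next dose Group if any of the stopping criteria listed in" Section 8.5 are met. Section 8.6.2 says "If no criteria for halting the study are met (see Section 8.5 above) vaccinations will proceed with approval from the SMC".

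**The concern.** An exemption written into one criterion and absent from a broader one joined to it by OR does no work. The fifth criterion signals that isolated large local reactions should not by themselves stop vaccination; the sixth, read literally, stops it for exactly those reactions. Two people applying the text in good faith could reach different answers for the same three children.

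The urticaria point is similar. The third and fourth criteria turn on a grade, and the protocol has two scales on which urticaria can be placed. If the scale is not named, whether a criterion is met can depend on the table consulted. Urticaria matters here because Section 1.1.3 reports that generalized urticaria stopped vaccinations in an earlier trial of a different, larval-stage hookworm antigen.

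At stake is consistent application of the pre-specified rule that governs suspension and dose escalation in children aged 6 to 10. No sample size, significance level or estimate depends on it.

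**Working it through.** **1. The plan's own safety probabilities.** Section 10.1 tabulates the chance of at least one event, 1 − (1 − p)^n. For n = 20 and p = 10% this is 1 − 0.90^20 = 87.84%, as printed; the other 14 cells also reproduce. The plan gives no comparable figures for the halting criteria.

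**2. Is the fifth criterion contained in the sixth?**

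| Element | Fifth criterion | Sixth criterion |
|---|---|---|
| Children in one Group | 3 or more | 3 or more |
| Clinical grade | 3 or higher (Grade 3 is the top of the scale in Section 8.2.1) | 3 |
| Laboratory grade | 3 or higher | 2 or higher |
| Relatedness | probable, definite | possible, probable, definite |
| Exemption | isolated Grade 3 erythema or swelling | none |

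On every row the sixth is at least as wide. Three further statements show that the exempted events fall inside it:

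- Section 8.2.2 says reactogenicity events are adverse events.
- The line listings in Section 10.3 class clinical and laboratory adverse events as immediate, systemic or local, so local events belong among the clinical ones.
- Section 8.2.2 fixes relatedness as definite for local reactions within 14 days.

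As a mechanical check, take 4 event types (erythema/swelling, other objective finding, subjective symptom, safety laboratory value) × 3 grades × 5 relatedness categories × counts of 0 to 20, which is 1,260 combinations. None meets the fifth criterion without the sixth, and deleting the exemption changes the halting decision in none.

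**3. How often might this matter?** The trigger is 3 of 20 children in a Group (15%), or 3 of the 16 hookworm vaccinees (18.75%). The documents give no rate of Grade 3 erythema or swelling with these vaccines in children, so the per-child rates below are assumptions.

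P(X ≥ 3) = 1 − Σ C(n,k) p^k (1 − p)^(n − k), summed over k = 0, 1, 2.

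For n = 20, p = 5%: 1 − (0.35849 + 0.37735 + 0.18868) = 0.0755.

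| Assumed rate | n = 16 | n = 20 |
|---|---|---|
| 1% | 0.05% | 0.1% |
| 5% | 4.3% | 7.5% |
| 10% | 21% | 32% |

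If the exemption governed the sixth criterion too, isolated erythema or swelling would contribute nothing.

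**4. Urticaria on the two scales.**

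| Presentation | Table 2 (solicited) | Table 3, hypersensitivity row (headed unsolicited) |
|---|---|---|
| No medication needed | Grade 1 | Grade 2 if regarded as mild urticaria |
| Intravenous medication or steroids beyond 24 hours, no bronchospasm | Grade 3 | Does not meet Grade 3, which needs symptomatic bronchospasm |

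Two probably related untreated cases may therefore meet the fourth criterion on Table 3 but not on Table 2. One possibly related case treated beyond 24 hours meets the third on Table 2 but not on Table 3. Where that case is also a serious adverse event, the first criterion applies at the same relatedness threshold and the conflict disappears.

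**5. Expected frequency of urticaria.** The only rate in the documents is 0.1%, for hepatitis B vaccine (section on aluminum-based adjuvants). Applied to 3 × 16 = 48 hookworm vaccinees:

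- one or more cases: 1 − 0.999^48 = 4.7%;
- two or more cases: 0.1%.

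Both cover urticaria of any kind, so at that rate they are upper bounds for the presentations in step 4.

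**The case against.** **The error in the fifth and sixth criteria is on the cautious side.** This stands. The worst effect is an added suspension, and Section 8.6.2 requires written SMC approval before Groups 2 and 3 in any case. A reader might infer from Section 3 that three isolated Grade 3 erythema cases would bar the next Group outright. The documents do not support that: Sections 4.3.6 and 8.5 describe suspension pending review with the option to resume, and Section 3 can be read consistently with them. What remains is that its wording is stricter than theirs.

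**The exemption could be read into the sixth criterion, or clinical adverse events could be read as excluding local ones.** Neither is written, and the listings in Section 10.3 speak against the second.

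**Only Table 3 has a hypersensitivity row, so it is the natural source for the third and fourth criteria.** This largely stands. A reader might infer that urticaria simply carries two contradictory grades. That is too strong: the tables use different axes, and nothing equates needing no medication with being mild. But Table 3 is headed for unsolicited events while urticaria is solicited, and it has no explicit entry for urticaria that is more than mild without bronchospasm (Grade 2 at most, if read as a pruritic rash).

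**The prolonged-treatment case is narrow.** This stands. Intravenous treatment beyond 24 hours would often involve an overnight stay, which makes the event serious under Section 8.2.3. Mainly outpatient steroid treatment is left.

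**Other safeguards exist.** This also stands. A reader might infer a gap in safety oversight. There is none: Section 8.5 lets the Independent Medical Monitor hold the study at any time, SMC review continues, and Section 4.3.4 has individual withholding rules.

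**White-cell grading.** A reader might infer that the Grade 3 cell for raised white-cell counts in Table 5 is unusable, because its sign points the wrong way in the available text. That part of the table is disturbed by text extraction, so the sign may be an artefact or an evident slip. No conclusion rests on it.

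**Conclusion.** The point holds as a wording defect that should be fixed before enrolment.

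- **Exemption.** On the current text the fifth criterion lies wholly within the sixth, so the exemption has no effect. This follows from Sections 8.2.2, 8.5 and 10.3 and needs no assumed rate. Three exempted cases among the 20 children of a Group trigger suspension pending review. The chance of that, 0.1% to 32% for n = 20, rests entirely on assumed rates of 1% to 10%.
- **Urticaria.** This is a smaller defect: a missing table reference, complicated by the heading of Table 3. It can change whether the third or fourth criterion is met, except where the event is also serious and the first applies. Such cases should be rare. Sections 1.1.4 and 1.1.6 report no IgE to Na-GST-1 above the clinical cut-off or detectable in those tested, and Section 1.1.8 reports IgE to the inactivated Na-APR-1 in 0.6%.

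The consequence is inconsistent application of a pre-specified rule. Safety oversight and the statistical design are intact.

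**What to change.** Before enrolment the sponsor and the SMC should:

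1. Reconcile the fifth and sixth criteria of Section 8.5 on isolated Grade 3 erythema or swelling, or state which governs.
2. State which table grades urticaria for the third and fourth criteria, so that each presentation has exactly one grade for that purpose.
3. Reconcile the consequence worded in Section 3 with Sections 4.3.6 and 8.5.

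Which rule, grade or threshold applies is for them to decide.

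Two queries can be handled at the same time. Check the Grade 3 sign for raised white-cell counts in Table 5 against the PDF. Close the single-value gaps where no table grade is listed: exactly 39.0°C (Table 2), and hemoglobin 7.0 g/dL and creatinine 1.8 mg/dL (Table 5).

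The cost is an amendment to protocol text and tables, agreed with the SMC. It needs no extra visits, samples or assessments.

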8.6 Safety Oversight

8.6.1 Independent Medical Monitor (IMM)

An independent Medical Monitor will be appointed for oversight of subject safety in this trial. The IMM will be a local, qualified physician who will be available to advise the investigators on trial-related medical questions or problems. The IMM will work with the study team to ensure adequacy of adverse event monitoring and reporting. Should the IMM not be available, he/she will recommend an alternative to serve as a substitute IMM.

The IMM's primary responsibility will be to monitor subject safety. The Principal Investigator is responsible for ensuring that the IMM is aware of any new safety information that becomes available during the course of the trial.

8.6.2 Safety Monitoring Committee (SMC)

At least three individuals will be selected to serve as the study Safety Monitoring Committee (SMC) to advise the Sponsor and the study investigators on the trial. All SMC members will be independent from the Sponsor and study site. The SMC's primary responsibility will be to monitor subject safety. The Principal Investigator is responsible for ensuring that the SMC is aware of all new safety information. The SMC will periodically review data on safety and enrollment, and will review cumulative safety data for evidence of study related AEs, adherence to the protocol, and factors that may affect outcome or study data such as protocol violations and losses to follow up.

Cumulative safety data reports from the trial will be submitted to the SMC before beginning vaccinations in Group 2 and Group 3 of the study. These safety data reports will include data from at least the first 14 days after first vaccination of all subjects in the prior Group. After the third and final vaccination has been administered to all cohorts, additional safety and immunology results and reports will be submitted to the SMC as they become available.

Conference calls between the investigators and the SMC will be scheduled at least one week prior to beginning vaccinations in Group 2 and Group 3 of the study. If no criteria for halting the study are met (see Section 8.5 above) vaccinations will proceed with approval from the SMC.

Written approval (via fax or email) to proceed to vaccinating Group 2 and Group 3 must be obtained from the SMC prior to vaccine administration. Both the SMC and IMM will have access to the randomization code, as they may wish to review the data in an unblinded fashion should significant safety questions arise prior to the final unblinding of the study.

It is the Principal Investigator's (or designated agent) responsibility to ensure that the SMC reviews the current safety data (grouped by dose cohort), study protocol, and any other requested documents at its meetings. Occurrence of an SAE will be reported to the SMC at the same time

that it is reported to the IRB. Additionally, any new information that may adversely affect the safety of the subjects or the conduct of the study will be submitted to the SMC as it becomes available.

